# 3.5.5.2 Safety Analysis Population

The All Patients as Treated (APaT) population will be used for the analysis of safety data in this study. The APaT population consists of all randomized patients who received at least one dose of study treatment. Patients will be included in the treatment group corresponding to the study treatment they actually received for the analysis of safety data using the APaT population. For most patients, this will be the treatment group to which they are randomized. Patients who take incorrect study treatment for the entire treatment period will be included in the treatment group corresponding to the study treatment actually received.

At least one laboratory or vital sign measurement obtained subsequent to at least one dose of study treatment is required for inclusion in the analysis of each specific parameter. To assess change from baseline, a baseline measurement is also required.

Details on the approach to handling missing data for safety analyses are provided in Section 3.5.6 (Statistical Methods).

#### 3.5.6 Statistical Methods

Statistical testing and inference for safety analyses are described in 3.5.6.2. Efficacy results that will be considered to be statistically significant after consideration of the strategy for controlling the Type I error are described in Section 3.5.6.1 (Multiplicity). Nominal p-values may be (will be) computed for other efficacy analyses as a measure of strength of association between the endpoint and the treatment effect rather than formal tests of hypotheses. Unless otherwise stated, all statistical tests will be conducted at the  $\alpha$ =0.05 (2-sided) level.

# 3.5.6.1 Statistical Methods for Efficacy Analyses

The primary efficacy analysis will compare the caspofungin treatment group to the amphotericin B deoxycholate treatment group with respect to the proportion of patients with fungal-free survival at the 2-week posttherapy period. The minimum criterion for success is that the lower bound of 95% CI for the difference between the 2 treatment groups (caspofungin minus amphotericin B deoxycholate) in the primary efficacy endpoint is >0.

**Protocol/Amendment No.:** 064-02

The treatment comparisons for the primary and secondary efficacy analyses will be made using the difference in response rates between the 2 treatment groups and its 95% confidence interval. The confidence interval for the difference in response rates will be calculated using a methodology proposed by Miettinen and Nurminen [17].

Patients who have missing data for a given endpoint at the timepoint of interest will be counted as a failure for that endpoint at that timepoint.

Also, the caspofungin efficacy results from this study will be compared descriptively to the efficacy results for patients with invasive candidiasis in a prior Phase II pediatric documented infection study (Protocol 043, children and adolescents aged 3 months to 17 years) and prior Phase III adult studies (Protocols 014 and 801).

Table 3-6 summarizes the key efficacy analyses.

**Protocol/Amendment No.:** 064-02

Table 3-6
Analysis Strategy for Key Efficacy Variables

En du sint/Mariable	Primary vs.		A malania	Missing Data		
Endpoint/Variable (Description, Time Point)	Supportive Approach †	Statistical Method	Analysis Population	Missing Data Approach		
Primary						
Proportion of patients with fungal-free survival through the 2-week posttherapy period	P	Miettinen and Nurminen method	FAS	A patient with missing data will be considered a failure.		
Proportion of patients with fungal-free survival through the 2-week posttherapy period	S	Miettinen and Nurminen method	PP	Observed data		
Secondary						
Proportion of patients reporting fungal-free survival at the end of study therapy	P	Miettinen and Nurminen method	FAS	A patient with missing data will be considered a failure.		
Proportion of patients reporting fungal-free survival at the end of study therapy	S	Miettinen and Nurminen method	PP	Observed data		
P=Primary approach; S=Secondary approach.						

# 3.5.6.2 Statistical Methods for Safety Analyses

Safety and tolerability are assessed by clinical review of all safety parameters, including adverse experiences and laboratory values.

The analysis of safety results will follow a tiered approach (Table 3-7). The tiers differ with respect to the analyses that will be performed. Safety parameters or adverse experiences of special interest that are identified *a priori* constitute "Tier 1" safety endpoints that will be subject to inferential testing for statistical significance with p-values and 95% CI provided for between-group comparisons. Other safety parameters

**Protocol/Amendment No.:** 064-02

will be considered Tier 2 or Tier 3. Tier 2 parameters will be assessed via point estimates with 95% CI provided for between-group comparisons; only point estimates by treatment group are provided for Tier 3 safety parameters.

Adverse experiences (specific terms as well as system organ class terms) that are not prespecified as Tier-1 endpoints will be classified as belonging to "Tier 2" or "Tier 3", based on the number of events observed. Membership in Tier 2 requires that at least 4 patients in any treatment group exhibit the event; all other adverse experiences will belong to Tier 3.

The threshold of at least 4 events was chosen because the 95% confidence interval for the between-group difference in percent incidence will always include zero when treatment groups of equal size each have less than 4 events and thus would add little to the interpretation of potentially meaningful differences. Because many 95% confidence intervals may be provided without adjustment for multiplicity, the confidence intervals should be regarded as a helpful descriptive measure to be used in review, not a formal method for assessing the statistical significance of the between-group differences in adverse experiences and predefined limits of change.

Continuous measures such as changes from baseline in laboratory, vital signs, and ECG parameters that are not pre-specified as Tier-1 endpoints will be considered Tier 3 safety parameters. Summary statistics for baseline, on-treatment, and change from baseline values will be provided by treatment group in table format.

P-values (Tier 1 only) and 95% confidence intervals (Tier 1 and Tier 2) will be provided for between-treatment differences in the percentage of patients with events; these analyses will be performed using the Miettinen and Nurminen method (1985), an unconditional, asymptotic method. For this protocol, there are no Tier 1 events.

**Protocol/Amendment No.:** 064-02

Table 3-7
Analysis Strategy for Safety Parameters

Safety Tier	Safety Endpoint a	p-Value	95% CI for Treatment Comparison	Descriptive Statistics
Tier 1	None			
Tier 2	Any AE Any Serious AE Any Drug-Related AE Any Serious and Drug-Related AE Discontinuation due to AE Discontinuation due to a Drug-Related AE Specific AEs, SOCs, or PDLCs b (incidence ≥4 in one of the treatment groups)		X X X X X X	X X X X X X
Tier 3	Specific AEs, SOCs or PDLCs b (incidence <4 in all of the treatment groups) Change from Baseline Results (Labs, ECGs, Vital Signs)			X X

<sup>a Adverse Experience references refer to both Clinical and Laboratory AEs.

Note: SOC=System Organ Class; PDLC=Pre-Defined Limit of Change; X = results will be provided.

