#### 1.5 SAMPLE

Approximately 90 patients with documented invasive candidiasis will be randomized in a 2:1 ratio (caspofungin: amphotericin B deoxycholate), as specified in Table 1-1 below. All doses of study drug will be administered intravenously as a single once-daily dose.

Table 1-1
Protocol 064 Treatment Groups

Treatment		
Group	Regimen	Number of Patients
Group 1	Caspofungin at 2 mg/kg (per body weight) once daily	~60
Group 2	Amphotericin B deoxycholate at 1 mg/kg (per body weight) once daily	~30

In an effort to strive for adequate representation of patients from different weight groups (reflective of patient gestational age) in both treatment arms, randomization will be stratified into 3 weight categories (based on weight at study entry): <1000 grams, 1000 to 1500 grams, and >1500 grams. Patients will be stratified into each of the weight categories in a manner consistent with the 2:1 randomization of caspofungin to amphotericin B deoxycholate.

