### Amphotericin B Use in Neonates and Infants Less than 3 Months of Age

The IDSA clinical practice guideline for the management of candidiasis [29] recommends amphotericin B deoxycholate as the first-line treatment for invasive candidiasis in neonates/young infants at a dose of 1 mg/kg/day. Publications describing prospective, randomized, comparator-controlled trials of amphotericin B deoxycholate in neonatal candidiasis are predominantly limited to three studies, each enrolling less than 60 patients in total and less than 35 in the amphotericin B deoxycholate treatment groups, as shown in Table 3-3. Measurements of treatment success, which varied among these studies, ranged from 41.7% to 67.6% for the amphotericin B deoxycholate group. Although limited in population sizes, two of these studies showed that patients treated with amphotericin B deoxycholate had more findings of hepatotoxicity, namely elevated alkaline phosphatase and total serum bilirubin, than comparators [9, 24]. As noted comparator-controlled trial of caspofungin versus amphotericin B deoxycholate, greater rates of drug-related laboratory abnormalities were also observed in patients who received amphotericin B deoxycholate than those who received caspofungin (see Table 3-1) [9]. Nephrotoxicity is generally the most concerning side effect for neonates [27]; however, it has been reported that nephrotoxicity associated with amphotericin B deoxycholate use in infants and children is generally less severe than in adults, likely due to the more rapid clearance in children [25]. In addition, evidence suggests that amphotericin B deoxycholate is generally well tolerated in premature infants [26, 27]. For this reason, liposomal preparations are not generally used in this patient population.

**Protocol/Amendment No.:** 064-02

Table 3-3

Clinical Trials of Amphotericin B Deoxycholate in the Neonatal Population

	Study Description	Dose of Amphotericin B	
Publication	(Year Conducted)	Deoxycholate	Findings
Mohamed	Caspofungin vs.	1 mg/kg/day	• See Table 3-1
WA and	amphotericin B deoxycholate		Nephrotoxicity was seen in 11.8%
Ismail M	(October 2008 to		(2/17 patients) in the amphotericin
[9]	September 2010)		B deoxycholate group and 0% in caspofungin group
Dreissen	Fluconazole vs.	1 mg/kg/day	Neonates <3 months of age were
M, et al.	amphotericin B	1 1118/118/ 444)	eligible for enrollment
[24]	deoxycholate		• In total, 24 neonates were enrolled,
	(June 1992 to June 1993)		with 11 patients receiving

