# 3.5.8.2 Sample Size and Power for Safety

In a previous pediatric study (Protocol 043) in which 38 patients (aged 6 months to 17 years, mean 8 years) with invasive candidiasis were treated with caspofungin, the

**Protocol/Amendment No.:** 064-02

proportion of patients with one or more drug-related adverse experiences was 23.7%. With this figure as a guide and the assumption that experience in neonates/infants is similar to that of the pediatric patients, a drug-related adverse experience rate of  $23.7 \pm 10.8\%$  (95% CI calculated using the binomial distribution) is projected for 60 patients in the caspofungin treatment group.

While the above is the projected drug-related adverse experiences rate based on a previous study rate, it does not address possible study outcomes based on an observed number of adverse experiences within each treatment group. Given anticipated sample sizes of 60 patients on caspofungin and 30 patients on amphotericin B deoxycholate, Table 3-9 summarizes the difference (caspofungin – amphotericin B deoxycholate) and 95% CI for the difference for possible drug-related adverse experience outcome combinations.

**Protocol/Amendment No.:** 064-02

Table 3-9

Difference (Caspofungin – Amphotericin B Deoxycholate) and 95% Confidence Interval for the Differences a for Possible Drug-Related Adverse Experience Outcome Combinations

Caspofungin Therapy (N = 60)	Amphotericin B Deoxycholate Therapy (N = 30)					
N Events (%)	3 (10.0)	6 (20.0)	9 (30.0)	12 (40.0)	15 (50.0)	18 (60.0)
3 (5.0)	-5.0 (-21.2, 5.9)	-15.0 (-32.9, - 1.8)	-25.0 (-43.5, - 9.7)	-35.0 (-53.4, -18.0)	-45.0 (-62.6, - 26.8)	-55.0 (-71.2, -36.1)
6 (10.0)	0.0 (-16.7, 12.4)	-10.0 (-28.4, 4.6)	-20.0 (-39.1, - 3.5)	-30.0 (-49.0, -11.9)	-40.0 (-58.2, - 20.8)	-50.0 (-67.0, -30.2)
9 (15.0)	5.0 (-12.1, 18.4)	-5.0 (-23.9, 10.5)	-15.0 (-34.6, 2.4)	-25.0 (-44.5, -6.2)	-35.0 (-53.8, - 15.1)	-45.0 (-62.6, -24.5)
12 (20.0)	10.0 (-7.6, 24.1)	0.0 (-19.4, 16.2)	-10.0 (-30.1, 8.0)	-20.0 (-40.0, -0.6)	-30.0 (-49.4, -9.6)	-40.0 (-58.2, -19.0)
15 (25.0)	15.0 (-3.0, 29.6)	5.0 (-14.8, 21.7)	-5.0 (-25.5, 13.4)	-15.0 (-35.5, 4.8)	-25.0 (-44.9, -4.2)	-35.0 (-53.7, -13.7)
18 (30.0)	20.0 (1.7, 34.9)	10.0 (-10.2, 27.0)	0.0 (-20.9, 18.7)	-10.0 (-30.8, 10.1)	-20.0 (-40.3, 1.1)	-30.0 (-49.2, -8.4)
21 (35.0)	25.0 (6.4, 40.0)	15.0 (-5.5, 32.1)	5.0 (-16.2, 23.9)	-5.0 (-26.2, 15.3)	-15.0 (-35.6, 6.3)	-25 (-44.6, -3.2)
a Calculated using the Miettinen and Nurminen method.						

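### The four-patient cut-off for giving adverse events a confidence interval rests on equal group sizes, and fails at 60:30 for events seen only on amphotericin B

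*Combined protocol and SAP*

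**What the plan says.** Section 3.5.6.2 sorts adverse events into tiers. There are no Tier 1 events. For specific terms, "Membership in Tier 2 requires that at least 4 patients in any treatment group exhibit the event". Tier 2 terms get a Miettinen-Nurminen 95% CI for the difference between arms. For the rest, "only point estimates by treatment group are provided for Tier 3 safety parameters". Table 3-7 repeats the rule: specific AEs, system organ classes (SOCs) and predefined limits of change (PDLCs) with "incidence <4 in all of the treatment groups" are Tier 3. The same table places six broad AE categories in Tier 2 by name, whatever their counts.

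The cut-off of 4 is explained by one property, namely that the interval "will always include zero when treatment groups of equal size each have less than 4 events and thus would add little" to the interpretation of differences.

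The design is not equal. Section 1.5 states: "Approximately 90 patients with documented invasive candidiasis will be randomized in a 2:1 ratio". The safety projections in Section 3.5.8.2 begin: "Given anticipated sample sizes of 60 patients on caspofungin and 30 patients on amphotericin B deoxycholate". No section adapts the cut-off or its rationale to 2:1 allocation.

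**The concern.** The rule is meant to leave out intervals that cannot exclude zero. Its justification is limited to equal groups. With 60 and 30 patients the same count means different things in the two arms: 4 patients are 4/60 = 6.7% on caspofungin but 4/30 = 13.3% on amphotericin B. An event confined to the smaller arm could therefore fall below the cut-off while its interval excludes zero. An event confined to the larger arm could pass the cut-off when its interval cannot.

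At stake is whether a reader of the safety tables sees an interval for a specific event that occurs only on the comparator. Because no event is in Tier 1, a specific term has no other prespecified route to a between-group interval.

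**Working it through.** **Inputs.** Arms of 60 and 30 (Section 3.5.8.2); Miettinen-Nurminen 95% intervals and the Tier 2 cut-off of 4 (Section 3.5.6.2); amphotericin B nephrotoxicity of 2/17 = 11.8% (Table 3-3). The caspofungin event rates used below are assumptions.

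**Step 1: reproduce the plan's figures.** The score interval without the N/(N-1) variance factor reproduces all 84 limits in Table 3-9 to one decimal, for example 3/60 vs 3/30 = -5.0 (-21.2, 5.9). With the factor, limits differ by at most 0.16 points. Both versions were used below and lead to the same conclusions at 60:30.

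**Step 2: confirm the property for equal groups.** The interval excludes zero when |z| > 1.96 at zero difference, where

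z = (p1 - p2) / sqrt[ p(1 - p)(1/n1 + 1/n2) × N/(N - 1) ], with p the pooled proportion and N = n1 + n2.

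For 0/60 vs 3/60: p = 3/120 = 0.025, so z = -0.05 / sqrt(0.025 × 0.975 × 0.0333 × 120/119) = -1.75. The interval includes zero. With 30, 45 and 60 per arm, the upper limits for 0 vs 3 are +2.1, +1.6 and +1.2 points. With 4 vs 0 the interval excludes zero (60 per arm: -16.0 to -0.4). So a cut-off of 4 is right for equal groups of this order.

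**Step 3: apply it at 60:30.**
- 0/60 vs 3/30: p = 3/90, z = -0.1 / sqrt(0.0333 × 0.9667 × 0.05 × 90/89) = -2.48.
- 0/60 vs 2/30: p = 2/90, z = -0.0667 / sqrt(0.0222 × 0.9778 × 0.05 × 90/89) = -2.01.
- 1/60 vs 3/30: p = 4/90, z = -0.0833 / sqrt(0.0444 × 0.9556 × 0.05 × 90/89) = -1.80.

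| Caspofungin | Amphotericin B | Difference, points | 95% CI with factor | 95% CI as in Table 3-9 |
|---|---|---|---|---|
| 0/60 | 3/30 | -10.0 | -25.7, -3.4 | -25.6, -3.5 |
| 0/60 | 2/30 | -6.7 | -21.4, -0.3 | -21.3, -0.4 |
| 1/60 | 3/30 | -8.3 | -24.2, +0.8 | -24.1, +0.8 |
| 0/60 | 1/30 | -3.3 | -16.8, +2.9 | -16.7, +2.8 |

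Of all pairs with 0 to 3 events per arm, only the first two exclude zero.

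**Step 4: sensitivity to arm sizes** (upper limits, with the factor).

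| Arms | 0 vs 3 | 0 vs 2 |
|---|---|---|
| 56:28 | -3.69 | -0.34 |
| 59:31 | -3.11 | -0.01 |
| 58:32 | -2.72 | +0.28 |

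The 0-vs-3 result is robust. The 0-vs-2 result is borderline.

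**Step 5: the other direction.** 4/60 vs 0/30 gives +6.7 (-5.1, 16.0), and 7/60 vs 0/30 gives +11.7 with a lower limit of -0.2. The first caspofungin-only count to exclude zero is 8/60 (1.4, 24.2). Counts of 4 to 7 qualify for Tier 2, yet their intervals all include zero.

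**Step 6: how often it could matter.** For an event at the 2/17 rate, a binomial with n = 30 gives P(2) = 0.181 and P(3) = 0.225, sum 0.406. Multiply by (1 - r)^60, the chance of no caspofungin events at true rate r.

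| Assumed r | 0 vs 2 or 3 | 0 vs 3 only |
|---|---|---|
| 0% | 41% | 23% |
| 1% | 22% | 12% |
| 2% | 12% | 7% |
| 5% | 2% | 1% |

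**The case against.** The best case for leaving the rule alone is that little depends on it. The section itself calls these intervals descriptive and unadjusted. The six endpoints of the secondary safety objective are in Tier 2 by name. A reader who sees 0/60 and 3/30 can compute the interval. No excess on the study drug loses an interval that would exclude zero; only comparator-only events are affected. Intervals for 4 to 7 caspofungin events against none still inform through their upper limits of 16 to 22 points. All of this stands, and it keeps the point small.

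The robust failure is a single cell. For 0/60 vs 2/30, Fisher's exact p is 0.109, against 0.035 for 0 vs 3. The 41% in Step 6 needs a true caspofungin rate of zero and counts the borderline cell. It also rests on 2 events in 17 patients at one site, while exclusion criterion 14 removes some patients at renal risk. At that same rate the amphotericin B arm would reach 4 or more events about 48% of the time and get an interval anyway. These probabilities are therefore illustrations only.

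A lower cut-off would also add mostly intervals that include zero. If both arms share one true rate, 69%, 93% and 99% of the added intervals would include zero at rates of 2%, 5% and 10%. That is a real cost, but it does not rescue a justification that is false for this allocation.

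**Conclusion.** The point holds. The only reason given for the cut-off depends on equal groups, and at 60:30 it is wrong for two patterns: clearly for 0 vs 3, where the upper limit is about 3.4 points below zero, and narrowly for 0 vs 2, where it is 0.3 to 0.4 points below. The failure is one-sided. It withholds the interval from an event at 10% against 0% on the comparator, and supplies one for caspofungin-only counts that cannot exclude zero.

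The effect is confined to the descriptive display of specific AEs, SOCs and PDLCs. Point estimates are still shown and no formal inference changes. The 0-vs-3 finding does not depend on the variance version or on modest drift in arm sizes. The 0-vs-2 finding assumes arms close to 60:30.

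**What to change.** In Section 3.5.6.2 and Table 3-7, define Tier 2 for specific AEs, SOCs and PDLCs as at least 4 caspofungin patients or at least 2 amphotericin B patients with the event. Replace the rationale with one that is true here: at 60:30, with at most 3 caspofungin and at most 1 amphotericin B patients affected, every interval includes zero. No interval now planned is removed. If the arms drift to about 58:32, the rule shows one interval that includes zero (0 vs 2) and misses none that excludes it. Because tier membership depends on observed counts, make the change before unblinding.

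The cost is wording in two places and more unadjusted descriptive intervals. If a term has the same true rate r in both arms (assumed), the chance that it moves from Tier 3 to Tier 2 is P(at most 3 of 60) × P(2 or 3 of 30):
- r = 2%: 0.968 × 0.118 = 11%
- r = 5%: 0.647 × 0.386 = 25%
- r = 10%: 0.137 × 0.464 = 6%

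A cut-off of 3 amphotericin B patients would move fewer terms (2%, 8% and 3%) and still cover the robust 0-vs-3 pattern. It would leave 0 vs 2 without an interval, so the plan's own criterion would still not quite hold at 60:30. The existing caution about unadjusted intervals already covers the additions.

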#### 3.5.6.3 Summaries of Baseline Characteristics and Demographics

The comparability of the treatment groups with respect to baseline characteristics will focus on clinical (rather than statistical) equivalence of the treatment groups. No statistical hypothesis tests will be performed on these characteristics. Mean, median, standard deviation, and range will be tabulated for characteristics which are continuous. Characteristics which are categorical, such as gender and race, will be summarized by count and percent.

#### 3.5.7 Multiplicity

No multiplicity adjustments are planned for any of the evaluations in this study.

## 3.5.8 Sample Size and Power Calculations

# 3.5.8.1 Sample Size and Power for Efficacy

This study will randomize approximately 90 patients at a 2:1 ratio into either the caspofungin treatment group (N = 60) or the amphotericin B deoxycholate treatment group (N = 30) and has 80% power to demonstrate the superiority of caspofungin over amphotericin B deoxycholate at an overall two-sided, 5% alpha-level, if the underlying treatment difference in fungal-free survival at 2 weeks posttherapy is approximately 30 percentage points (or larger). Randomization of approximately 90 patients should

b Includes only those endpoints not pre-specified as Tier 1 or not already pre-specified as Tier-2 endpoints.

**Protocol/Amendment No.:** 064-02

yield approximately 84 FAS evaluable patients, assuming an approximate 5% drop-out rate. The power and sample size are based on an underlying response rate of 50% for the amphotericin B deoxycholate treatment group, based on a review of the available data in the literature, including the recent comparative efficacy and safety study of caspofungin versus amphotericin B deoxycholate in which a favorable response was observed in 41.7% of amphotericin B deoxycholate-treated patients (see Table 3-1) [9]. On balance, the literature suggests most currently available antifungal agents are associated with successful outcomes in 40-80% of the patients [9, 24, 26, 30-36]; however, the efficacy with amphotericin B deoxycholate from the recent analysis was on the lower end (~40%) [9]. The caspofungin data from retrospective analyses and the recent comparative study demonstrated a relatively high success rate (80-100%) [9-13]. The minimum criterion for success is that the lower bound of 95% CI for the difference between the 2 treatment groups (caspofungin minus amphotericin B deoxycholate) in the primary efficacy endpoint is >0. Given the assumed response rate in the amphotericin B deoxycholate treatment group, this may occur when the observed difference between treatment groups is approximately 30 percentage points (or larger).

Assuming the same 2:1 randomization ratio and superiority hypothesis with 80% power, Table 3-8 displays sample size requirements for a few favorable response rate combinations, along with the difference and 95% CI for the difference.

Table 3-8

Superiority Sample Size Projections

Based on 80% Power and 2:1 (Caspofungin:Amphotericin B Deoxycholate)

Allocation Ratio

1 modulon runo					
Percent Favorable Caspofungin Response (A) 70 65	Percent Favorable Amphotericin B Deoxycholate Response (B) 40 40	Sample Size Projection Total (A:B) 93 (62:31) 137 (92:45) 218 (146:72)	Difference and 2-Sided 95% Confidence Interval for the Difference a (A – B) 30 (7.9, 48.1) 25 (7.5, 41.4) 20 (5.9, 33.2)		
80	50	84 (56:28)	30 (9.3, 50.3)		
75	50	127 (85:42)	25 (7.7, 42.2)		
70	50	206 (137:69)	20 (5.3, 33.1)		
90	60	66 (44:22)	30 (11.0, 53.6)		
85	60	105 (70:35)	25 (8.3, 43.8)		
80	60	177 (118:59)	20 (5.6, 33.9)		
a Calculated using the Miettinen and Nurminen method.					

